2.2 Study Agent

This study will use ^{68}Ga -RM2. This PET radiopharmaceutical has previously been identified as ^{68}Ga -DOTA Bombesin or BAY86-7548. This is not an FDA-approved product. This protocol is submitted to IND [REDACTED], the IND to which this protocol is submitted.

This study will also use ^{68}Ga -PSMA11. This PET radiopharmaceutical has previously been identified as DFKZ-11; HBED-CC PSMA; or the “Heidelberg compound.” This is not an FDA-approved product, and is described in detail in IND 128379.

2.3 Clinicaltrials.gov

This study will be registered on ClinicalTrials.gov.

2.4 Rationale

In this study, we propose to use a well-established PET isotope, Gallium-68 (^{68}Ga), bound to a PSMA ligand (ie, ^{68}Ga -PSMA-11) and a GRPR ligand (ie, ^{68}Ga -RM2) that have high affinity for prostate specific membrane antigen and gastrin releasing peptide receptors, respectively. Therefore, we propose the following goals:

1. To demonstrate that ^{68}Ga -RM2 and ^{68}Ga -PSMA-11 PET/MRI can detect additional cancers over mpMRI.
2. To demonstrate that ^{68}Ga -RM2 and ^{68}Ga -PSMA-11 PET/MRI can assess changes in response to treatment and predict PFS at 24 months.

^{68}Ga -RM2 at Stanford University: Under an FDA-approved IND (# █) our group currently uses ^{68}Ga -RM2 in 2 clinical scenarios, either prior to prostatectomy in patients with intermediate or high-risk PC or at biochemical recurrence after definitive treatment (prostatectomy or radiation therapy).

[figure not shown]

Figure 1. The uptake of ^{68}Ga -RM2 in a representative patient was localized in the anterior aspect of the prostate gland (arrows). This area correlated with PC (outlined in black) on corresponding prostatectomy sections.

^{68}Ga -RM2 identified primary PC lesions in all 15 patients scheduled for prostatectomy included in our pilot study [81]. An example is shown in **Figure 1**.

We recently published our results using ^{68}Ga -RM2 PET/MRI in 32 patients with biochemical recurrence of PC and negative conventional imaging (bone scintigraphy and CT or MRI) [66]. Currently, we have 80 participants scanned at BCR and our data indicates a 70% detection rate in this population with a mean PSA of 8.0 ng/dl and negative conventional imaging. The lowest PSA in a patient with positive ^{68}Ga -RM2 PET was 0.24. **One third of the lesions found on ^{68}Ga -RM2 PET were biopsied; all results were true positive.** Examples are shown in **Figure 2**. More importantly in our opinion, **PSA velocity values were $0.32 \pm 0.59 \text{ ng/ml/year}$ (range: 0.04-1.9) in patients with negative PET scans and**

$2.51 \pm 2.16 \text{ ng/ml/year}$ (range: 0.13-8.68) in patients with positive PET scans ($P=0.006$), suggesting the ability to detect more aggressive PC.

[figure not shown]

Figure 2. ^{68}Ga -RM2 uptake in pelvic nodal metastases in representative patients at BCR with various PSA levels. ^{68}Ga -RM2 lesion detection rate is 47.6% at PSA<1, 70% at PSA 1-2, 72.2% at PSA 2-5 and 90.3% at PSA>5 in our experience.

2.5 Study Design

This is a NCI-funded phase II study with a total of 100 participants with known prostate cancer, scheduled to undergo HDR local therapy. All patients will first be seen by a Stanford Cancer

Institute physician and then referred if appropriate on clinical grounds to Dr [name] or his colleagues for this study. Eligible participants will undergo baseline assessments at enrollment. The following steps will take place after the participant has signed the written consent (participants will be randomized to have ^{68}Ga -RM2 first followed by ^{68}Ga -PSMA11 within 2 weeks or ^{68}Ga -PSMA11 first followed by ^{68}Ga -RM2 within 2 weeks [50/50 chance for each schedule]). After the 1st scan, the 2nd scan will only occur after the follow-up with the patient for the 1st scan, and after a minimum of 3 days have elapsed.

Scan 1

1. Participants will be given a copy of the consent form s/he signed
2. Participant will be asked to drink 1 to 2 glasses of water before arrival at the clinic
3. Vital signs (heart rate, blood pressure) will be recorded
4. Participant will be injected IV with $140 \pm 20\%$ mBq of ^{68}Ga -RM2 **OR** 3 to 7 mCi of ^{68}Ga -PSMA11.
5. Participant will void immediately prior to the scan
6. Approximately 45 minutes after the radiopharmaceutical IV administration, data acquisition will begin in the pelvic region and move toward the head. First, localizer MRI scans will be performed to define the table positions. After correct positioning of the spatial acquisition windows is ensured, the combined PET/MRI acquisition will be initiated with 3 to 5 table positions at a 2 to 4-min acquisition time per table position.
7. Participants will be dismissed.
8. Vital signs (heart rate, blood pressure) will be recorded again at the completion of the study
9. Participants will be contacted at 24 to 72 hours following the scan in order to capture potential occurring Adverse Events.

Scan 2

1. Participant will be asked to drink 1 to 2 glasses of water before arrival at the clinic
2. Vital signs (heart rate, blood pressure) will be recorded
3. Participant will be injected IV with 3 to 7 mCi of ^{68}Ga -PSMA11 **OR** $140 \pm 20\%$ mBq of ^{68}Ga -RM2 (ie, the radiopharmaceutical not administered for Scan 1)
4. Participant will void immediately prior to the scan
5. Approximately 45 to 60 minutes after the radiopharmaceutical IV administration, data acquisition will begin in the pelvic region and move toward the head. First, localizer MRI scans will be performed to define the table positions. After correct positioning of the spatial acquisition windows is ensured, the combined PET/MRI acquisition will be initiated with 3 to 5 table positions at a 2 to 4 minute acquisition time per table position. Only MR sequences required for attenuation correction of PET data will be acquired.
6. Vital signs (heart rate, blood pressure) will be recorded again at the completion of the study.
7. Participants will be contacted at 24 to 72 hours following the scan in order to capture potential occurring Adverse Events.

The above will be repeated approximately 6 months after HIFU or HDR local treatment, prior to standard of care biopsy to evaluate for residual disease in the prostate.

Objectives of the Study

Primary Objectives

- To demonstrate that ⁶⁸Ga-RM2 and ⁶⁸Ga-PSMA-11 PET/MRI can detect additional cancers over mpMRI.
- To demonstrate that ⁶⁸Ga-RM2 and ⁶⁸Ga-PSMA-11 PET/MRI can assess changes in response to treatment and predict PFS at 24 months.

Secondary Objective

- None

Endpoints

Primary Endpoints

- Number of participants with assessable additional prostate cancer lesions over mpMRI
- Number of participants with assessable pre- and post-treatment uptake in response to HIFU or HDR local therapy

Secondary Endpoint

- None

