1. OBJECTIVE

Specific Aims

Aim 1: ^{68}Ga -RM2 PET/MRI and ^{68}Ga PSMA-11 PET/MRI detection of PC. We will investigate the performance of the new GRPr-binding PET radiopharmaceutical, ^{68}Ga -RM2, and compare it to the currently most widely investigated (but not FDA-approved) PC PET radiopharmaceutical, ^{68}Ga PSMA-11, as well as to mpMRI acquired during PET/MRI for the localization and staging of low-risk and intermediate-risk PC. New lesions identified on PET/MRI and not known from prior systematic prostate biopsy will be confirmed by targeted biopsy and GRPr and PSMA status will be evaluated with specific immunohistochemical stains [1, 2].

Aim 2: ^{68}Ga -RM2 PET/MRI and ^{68}Ga PSMA-11 PET/MRI prediction of PFS after local targeted therapy for PC. We will investigate if the combination of the GRPr-binding PET imaging agent, ^{68}Ga -RM2, and the most widely investigated (but not FDA-approved) PSMA-binding PET imaging agent, ^{68}Ga PSMA-11, together with mpMRI can predict PFS after local targeted therapy. We will determine if ^{68}Ga -RM2 PET/MRI and ^{68}Ga -PSMA-11 PET/MRI assessment at 6-months follow-up will predict PFS at 24 months based on standard clinical follow-up (PSA, imaging, tissue diagnosis).

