9.2 Data Management Plan

The CRFs will be stored in a locked office in the Nuclear Medicine clinic. Records will be kept using OnCore.

During the clinical investigation, the Protocol Director will evaluate the progress of the trial, including periodic assessments of data quality and timeliness, participant recruitment, accrual and retention, participant risk versus benefit, performance of trial sites, and other factors that can affect study

outcome. Monitoring of the trial will occur every 8 weeks and a record of monitoring activities will be maintained by the study team.

The Stanford Cancer Institute Data and Safety Monitoring Committee (DSMC) will audit study related activities to determine whether the study has been conducted in accordance with the protocol, local standard operating procedures, FDA regulations, and Good Clinical Practice (GCP). This may include review of regulatory binders, case report forms, eligibility checklists, and source documents. In addition, the DSMC will regularly review serious adverse events and protocol deviations associated with the research to ensure the protection of human subjects. Results of DSMC audits will be communicated to the IRB and the appropriate regulatory authorities at the time of continuing review, or in an expedited fashion, as needed.

10. Statistical Considerations and Evaluation of Results

10.1 Aim 1

Participants: 100 patients with low- or intermediate-risk prostate cancer, as described in the inclusion/exclusion criteria.

Design: Patients will have both ^{68}Ga -RM2 and ^{68}Ga -PSMA-11 PET/MRI, including mpMRI. mpMRI and PET images will each be evaluated separately. For each of the 12 prostate regions, between 1-3 imaging-positive samples will be taken, and 1 sample will be taken from each imaging-negative region.

Outcome measures: Number and location of lesions will be recorded for each modality in each patient. Gold standard will be based on the biopsy of lesions found on ^{68}Ga -RM2 and ^{68}Ga -PSMA-11 PET and prior systematic prostate biopsy, including IHC stains for GRPr and PSMA.

Hypothesis: ^{68}Ga -RM2 and ^{68}Ga -PSMA-11 PET/MRI sensitivity, either alone or in combination, will be higher than that of mpMRI alone.

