Reference standard: disease status of a lesion will be defined by biopsy of lesions found on ^{68}Ga -RM2 and ^{68}Ga -PSMA-11 PET and from prior saturation prostate biopsy. Tissue samples will be evaluated for GRPr and PSMA expression as previously reported [1, 2] and results will be compared to imaging findings. For GRPr staining, immunohistochemistry will be performed using standard protocols with primary rabbit polyclonal antibody (OPA1-15619, 1:200 dilution; Affinity Bioreagents, Golden, Colorado). For PSMA, a rabbit polyclonal anti-PSMA antibody (D7I8E; Cell Signaling technology, #12815, 1:100 dilution) will be used following the manufacturer's immunohistochemistry protocol. We already successfully used

these, as shown on page 11.

Drs. [name] (clinical pathologist), [name] and [name] will perform all histopathological analyses. Clinical follow-up will be gold standard if biopsy cannot be done.

Test to be evaluated: All T1w, T2w, DWI and DCE MR images will first be analyzed and graded by two-board certified abdominal radiologists with subspecialty training in body MRI and extensive clinical experience in prostate MRI (Drs. [name] and [name]) using the PI-RADS version 2 scoring system, blinded to the clinical information and pathology. The PET images will be corrected using the attenuation data from the MRI scan, and Drs. [name] and [name] who already have extensive experience with ^{68}Ga -RM2 and ^{68}Ga -PSMA-11 from our clinical trials, will perform blinded and random interpretation of the PET scans. Areas of focally increased ^{68}Ga -RM2 and ^{68}Ga -PSMA-11 uptake above surrounding background will be considered positive for PC (**Figures 9 and 10**). This approach is based on recently published guidelines for standard image interpretation developed for ^{68}Ga -PSMA-11 image interpretation [90]. In addition, semi-quantitative measurements of tracer uptake (SUV_{\max}) will be recorded for each lesion.

Statistical Analysis: The following statistical considerations have the full support of a biostatistician ([name]) within the Department of Radiology, who has been specifically assigned to the project and can provide continuous support throughout the data collection and data analysis process. He has also carefully reviewed the study design and was fully involved in the writing of this grant proposal.

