Because there may be multiple lesions per-patient and an indefinite number of non-lesions, the primary analysis will be per-region. Each of the 12 regions will have gold-standard positive or negative information, as well as imaging positive or negative assessments. Predictive accuracy of PI-RADS composite score (mpMRI) and SUV_{\max} PET uptake values will be assessed by ROC analysis using univariable logistic regression for the presence of PC. Areas under the entire ROC curve, and partial area at fixed 90% specificity will be compared. Additional benefit of the other modalities over mpMRI alone will be tested by a multivariable logistic regression. All analyses will be adjusted for clustering within patient.

Statistical Power and Sample Size: Based on our clinical experience at Stanford, we expect an average of 2 PC-positive regions and 10 PC-negative regions per patient. Assuming mpMRI has sensitivity of 80% and specificity of 80-90% [91], a sample size of 1200 regions with 20% prevalence will provide 90% power at 5% error to demonstrate non-inferiority of a PET sensitivity of 90% at 80-90% specificity [62, 92, 93].

The per-lesion analysis will depend on the number of lesions found but will be similar. We will also explore whether specific imaging findings are especially accurate in detection of specific subtypes of PC or prostate regions (i.e., peripheral versus transitional zones). It may also be the case that

predictive failures in imaging may be associated with a particular subtype. Given the small sample, we acknowledge that this analysis will be exploratory.

10.2 Aim 2

Participants: Those enrolled in Aim 1.

Design: Patients will be scanned with both ⁶⁸Ga-RM2 PET/MRI and ⁶⁸Ga-PSMA-11 PET/MRI at six months after initiation of therapy. MRI and PET images will each be evaluated separately.

Outcome measures: Changes in MRI features and/or changes in radiopharmaceutical uptake in lesions will be recorded for each modality in each patient. Gold standard of response to treatment and of PFS will be based on standard clinical follow-up (PSA, imaging, tissue diagnosis including IHC stains for GRPr and PSMA)

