10.3 Study Outcomes (ClinicalTrials.gov)

Primary Outcomes

Title: ⁶⁸Ga-RM2 and ⁶⁸Ga-PSMA-11 PET/MRI can detect additional cancers over mpMRI

Description: Detection of PC lesions will be assessed by ⁶⁸Ga-PSMA-11 and ⁶⁸Ga-RM2 PET scans. The outcome is the number of participants without dispersion, by randomization schedule, for which an assessment of PET-based PC lesions is successfully obtained.

Timeframe: 60 months

Safety outcome: No

Title: ^{68}Ga -RM2 and ^{68}Ga -PSMA-11 PET/MRI can assess changes in response to treatment and predict PFS at 24 months

Description: Therapeutic response to HDR will be assessed by ^{68}Ga -PSMA-11 and ^{68}Ga -RM2 PET scans. The outcome is the number of participants without dispersion, by randomization schedule, for which an assessment of PET-based therapeutic response to HDR is successfully obtained.

Timeframe: 84 months

Safety outcome: No

Secondary Outcome

None.

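### The first primary endpoint is not tied to the plan's own reference standard: Section 2.5 lets an unconfirmed PET-only lesion count, and Section 10.3 counts something else

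*Combined protocol and SAP*

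**What the plan says.** The first primary objective (Synopsis, Sections 2.4 and 2.5) is to show that PET/MRI with the two tracers finds cancers beyond those seen on mpMRI. Two texts define the matching endpoint:

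- Section 2.5, Primary Endpoints: "Number of participants with assessable additional prostate cancer lesions over mpMRI". The word for assessable is not defined and no reference standard is named.
- Section 10.3, first primary outcome: the number of participants, by randomization schedule, "for which an assessment of PET-based PC lesions is successfully obtained". No mpMRI comparison, positive finding or tissue result is required.

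Elsewhere the plan does provide for truth. Aim 1 in Section 1 states: "New lesions identified on PET/MRI and not known from prior systematic prostate biopsy will be confirmed by targeted biopsy". Section 10.1 samples imaging-positive regions and adds that "1 sample will be taken from each imaging-negative region". Under Reference standard it says that "disease status of a lesion will be defined by biopsy of lesions found on" either PET tracer, together with prior biopsy, and it falls back on clinical follow-up where biopsy cannot be done. The primary analysis there is per region, against that standard. Separately, under Test to be evaluated, focal "uptake above surrounding background will be considered positive for PC". Both 2.5 and 10.3 give no secondary endpoint.

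**The concern.** The objective is about cancers, whereas the endpoint in 2.5 is about lesions that can be assessed. If the count is taken from the PET read without a link to the biopsy result, a man whose only PET-only focus is a false positive can enter the numerator. A less specific tracer would then tend to give a larger count. The outcome in 10.3 fails differently: it approaches the number of men scanned, whatever the scans show. With no secondary endpoint to offset this, the reported headline could be high without bearing on the objective.

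**Working it through.** **Inputs (Section 10.1, Statistical Power and Sample Size).** The plan says "we expect an average of 2 PC-positive regions and 10 PC-negative regions per patient". mpMRI sensitivity is 80% and PET sensitivity 90%, each at 80-90% specificity. These are the figures behind the power statement: 90% vs 80% sensitivity at one-sided 5% and 90% power needs 237 positive regions (continuity-corrected), against 1200 x 0.20 = 240 in the plan.

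**Assumptions added here.** One tracer; equal specificities; PET and mpMRI err independently given disease status; regions within a man are independent. The plan states none of these.

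**Per region, P(PET positive, mpMRI negative).**
- Cancer region: 0.90 x 0.20 = 0.18.
- Benign region: 0.10 x 0.90 = 0.09 at 90% specificity; 0.20 x 0.80 = 0.16 at 80%.

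**Per man, which is the endpoint's unit.**
- At least one true PET-only region: 1 - 0.82^2 = 0.328.
- At least one false one: 1 - 0.91^10 = 0.611; 1 - 0.84^10 = 0.825.
- At least one of either kind: 1 - 0.82^2 x 0.91^10 = 0.738; 1 - 0.82^2 x 0.84^10 = 0.882.
- False only: 0.611 x 0.672 = 0.41; 0.825 x 0.672 = 0.55.
- Ratio of men with a false region to men with a true one: 0.611/0.328 = 1.9; 0.825/0.328 = 2.5.

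**Relaxing the assumptions.**

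| Scenario | Men with a true PET-only region | Men with a false PET-only region |
|---|---|---|
| Independent errors, equal specificities | 33% | 61-83% |
| Independent errors, any specificities within 80-90% | 33% | 57-86% |
| Latent (bivariate normal) correlation 0.5 between the tests | 27% | 50-70% |
| Within-patient ICC 0.1 (beta-binomial), independent errors | 31% | 48-70% |
| Within-patient ICC 0.3 (beta-binomial), independent errors | 28% | 33-52% |

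For the third row, the bivariate normal gives PET-only probabilities of 0.1485 per cancer region and 0.0676 or 0.1128 per benign region, so 1 - 0.8515^2 = 0.27, 1 - 0.9324^10 = 0.50 and 1 - 0.8872^10 = 0.70. In the last row at 90% specificity the ratio is 0.33/0.28, about 1.2.

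**Limits.** With dependence left wholly open, equal specificities allow 0.2-0.4 true and 0-2.0 false PET-only regions per man, so the marginal accuracies alone do not exclude a ratio of zero. If only the false positives were correlated, the per-region ratio would fall to 1:1 at a phi of 0.60 (90% specificity) or 0.78 (80%).

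**The 10.3 outcome.** None of this arithmetic applies to it. A scan with a false focus, a true focus or no focus contributes equally once an assessment is obtained.

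**The case against.** The strongest reply is that the plan already ties cancer to tissue. The endpoint speaks of prostate cancer lesions, Section 10.1 defines a lesion's disease status by biopsy, and Aim 1 says that new lesions "will be confirmed by targeted biopsy". The rule about uptake above background sits under the test to be evaluated, so it is the reading rule for the index test and not the definition of truth. The Aim 1 hypothesis, the ROC comparison and the power statement all use the gold standard, and false positives are penalised there.

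Most of this stands. A reader might infer that the plan directs a biopsy-benign focus to be counted as cancer. It does not: it is silent, and silence permits that count without prescribing it. A reader might also infer that the plan lacks histological truth, or that false positives inflate the 10.3 outcome. Neither is so.

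What the reply does not supply is the link. Aim 1 describes a procedure, the per-region analysis compares accuracy, and neither says which participants enter the count. The reply also leaves the conflict between 2.5 and 10.3 untouched.

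Two further cautions are fair. Regions are not lesions: a PET-only region may be the extension of a lesion that mpMRI shows next door. And Section 10.1 adjusts for clustering within patient but gives no ICC, so the independent-region figures are the high end for the share of men with a false region.

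**Conclusion.** The concern holds as a gap in the definition. Neither version of the first primary endpoint refers to the reference standard, the two versions count different things, and neither can show that PET detects additional cancers. Under the 2.5 wording, with the assumptions listed, about 74-88 of 100 men would be counted without confirmation, against about 33 with a true PET-only region.

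It is tempting to say that, on the plan's own figures, false additional cancers outnumber real ones by 2.5-4.4 to 1. That ratio is 0.90/0.36 to 1.60/0.36 regions per man. It is per region while the endpoint counts participants, and it needs equal specificities and independent errors that the plan does not state; mixed specificities alone widen it to 2.2-5.0. The participant ratio is about 1.9-2.5 under the same assumptions and near 1.2 at an assumed ICC of 0.3 with 90% specificity. The direction is the same in the scenarios tabulated; the size is an illustration, not a prediction.

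**What to change.** In Sections 2.5 and 10.3, use one definition: the number of participants with at least one PET-positive, mpMRI-negative lesion or region that is cancer by the Section 10.1 reference standard. That means biopsy, with clinical follow-up only where biopsy cannot be done, and participants who qualify on follow-up alone reported separately.

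Beside it, report PET-only lesions found benign and those left unverified, with the proportion confirmed. Give the counts per tracer (RM2, PSMA-11, either) rather than by randomization schedule, because every participant is to receive both. If the number of completed assessments is still wanted, report it as feasibility.

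No new procedure is needed: the biopsies and the per-modality lesion records are already planned. The costs are a smaller headline count and a change to the outcome wording intended for registration.
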